- Intraoperative angiography to assess anastomotic anatomy, patency and runoff

- Clinical duplex ultrasound: clinical assessment at all postoperative visits from Day 29 through Month 12 to assess HAV patency, mid HAV diameter and flow rate. The full length of the HAV should be imaged at each assessment to monitor for aneurysm development.
- High resolution duplex ultrasound intra-operatively and at Months 3, 6 and 12
- Endothelium-dependent, flow-mediated vasodilatation assessed by ultrasound (selected patients only at Day 29 and Month 12)
- Electrocardiogram (ECG; 12-lead): at screening
- Documentation of HAV interventions, surgical procedures and any complications immediately postoperatively through Month 12

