#### 7.4.2. Duplex ultrasound

Clinical duplex ultrasound examinations will be performed at Day 29 and Months 3, 6, 9, 12, 18, 24, 30, 36, 42, 48, and 54 and will follow standard bypass graft imaging protocols, including B-mode, power duplex and color duplex ultrasound imaging of the HAV with velocity spectral waveform analysis. The purpose of this clinical duplex ultrasound surveillance is to detect HAV stenosis and aneurysm development.

High-resolution duplex ultrasound imaging will be performed at Day 1 and Months 3, 6 and 12 to investigate the structural, mechanical and functional characteristics of the Humacyte HAV. This protocol will involve standard vascular lab imaging equipment and can be accomplished immediately following the clinical scan. The estimated additional scanning time is 15-20 minutes.

A subset of patients will also undergo endothelium-dependent flow-mediated vasodilation (EDFMV) testing of the HAV at Day 29 and Month 12. HAV diameter, time-averaged blood flow velocity and mean blood flow will be measured at baseline and during reactive hyperemia. The

percent change in HAV diameter during reactive hyperemia represents flow-mediated vasodilation, considered evidence of endothelial function.

Details of the procedure and the method of assessment of the images by a core lab will be given in a separate Imaging Procedures Manual.

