#### 7.5.2. Enrollment – Day 1 (HAV Implantation)

Prior to surgery the following assessments will be performed:

- Medical history (change from screening)
- Medication history (change from screening)
- Physical exam including surgical site (and HAV patency), number, size and location of ischemic lesions on the implant limb, and to evaluate any AEs
- Confirmation of eligibility (all screening results reviewed)
- Vital signs (heart rate, blood pressure, temperature oral, axillary or tympanic)
- Adverse events

Intraoperative Procedures:

- Implantation of HAV and documentation of surgical procedure, any complications (e.g., prolonged oozing at anastomoses), and interventions
- Confirmation of adequacy of anastomoses, patency and run-off by intraoperative angiography
- High-resolution duplex ultrasound of the HAV will be performed to provide a baseline for follow up measurements

#### 7.5.3. Follow-up Visits Day 5 through Month 12

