# 9.3. Efficacy Analyses

Primary, primary assisted, and secondary patency rates of the HAV at Month 12 and at all other post-surgery visits with evaluation of patency will be described.

Confidential

Primary patency is defined as the functional patency until any type of intervention; primary assisted patency is defined as an HAV still working without thrombosis; secondary patency is defined as the functional patency, with or without preceding successful interventional or surgical procedures to maintain or reestablish patency, until either final failure or the access is abandoned. Early discontinued patients prior to the visit of interest will be determined as being non-patent irrespective of the reason for discontinuation.

The rate and type of interventions needed to maintain / restore patency in the HAV will be descriptively tabulated.

The absolute change from baseline (Day 1) values to all post-surgery visits of duplex ultrasound parameters will be summarized. Summary statistics will also be provided at each time point.

The methods and endpoints regarding the efficacy parameters employed in this study are consistent with current clinical practice and are meaningful to the research community. Every attempt has been made to minimize the variability on the part of the surgeon when using this product. The results of this study will be used to determine the sample size of subsequent clinical studies.

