3.4 Interim Analysis

Data Monitoring Committee (DMC) reports will be provided during the course of the study.

Statistical Analysis Plan	Final Analysis
CLN-PRO-004	11/23

Endpoints will be assessed over a period of up to 60 months after HAV implantation.

- The **primary analysis** of the study will be based conducted on the earlier of a) when the final patient enrolled reaches 12 months post-implant or b) all subjects enrolled in the initial 36 month accrual period have reached 12 months post-implant. The SAP will call this the 1-year analysis.
- The **final analysis** will occur at the end of the study, when all patients have completed or exited the study.

The database extraction for the **1-year analysis** will include all study data collected at the time of the database extraction. The by-visit tables and figures will display all time points present in the data, including visits after the Month 12 visit (where applicable). Event tables (such as concomitant medications, AEs), will include all events during the study. Listings will display all study data available, including data collected after the Month 12 visit.

The database for the final analysis will include all study data and by-visit tables will display all study timepoints.

4 Statistical Evaluation

All tables, figures and listings will be produced using SAS (v9.4 or a more recent version).

Unless otherwise stated, categorical data will be presented using counts and percentages, whilst continuous parameters will be summarized using standard summary statistics as appropriate (n, mean, standard deviation [SD], median, minimum, maximum, 25th percentile, and 75th percentile). Minima and maxima will be quoted to the number of decimal places as recorded in the case report form (CRF); means, SDs and medians will be quoted to one further decimal place.

The closest non-missing values prior to implantation on Day 1 will be used as baseline values.

Unless otherwise stated, all confidence intervals will be presented as 95% two-sided intervals. For categorical endpoints, if all values are either success or failure, the exact CI will be presented.

As no sample size assessment has been undertaken, all analysis results are considered to be exploratory.

Details on the specification, definition, calculation and analysis of the efficacy and safety endpoint variables are given in Section 2 and the following sections.

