The assignment to a patency (yes/no) (primary, primary assisted, secondary patency) will be verified during the Data Review Meeting (DRM) using all data of CRF sections referring to HAV patency, clinical examination of the HAV site, doppler ultrasound assessment of HAV patency, HAV intervention, premature discontinuation, and AEs.

Patency rates will be presented with frequency tabulations showing patient numbers and patency rates for Month 12.

Clopper-Pearson confidence intervals (CI) will be presented for frequency counts of patency rates.

Kaplan-Meier (K-M) curves for primary, primary assisted, and secondary patency will be created at the 1-year report and for all subsequent reports. K-M curves will be provided using two censoring methods:

- a. Patients who die, withdraw from the study, or are lost to follow-up are censored at the day of the respective event.
- b. Patients who die, withdraw from the study, or are lost to follow-up are considered as having suffered failure of secondary patency at the day of the respective event.

Efficacy Objective #2:

Hemodynamically significant stenosis (>70% by duplex ultrasound criteria): The duplex ultrasound parameters will be summarized by planned visit up to Month 12.

- Frequency of stenosis occurrence, location of stenosis, and presence of aneurysm.
- Numeric summary of volumetric flow rate and inner diameter of HAV mid bypass.

A stenosis event can occur between planned study visits (i.e. Unscheduled Visits). A "by visit"

Statistical Analysis Plan	
CLN-PRO-004	

summary will represent the stenosis event/information that occurred before or on the planned visit. For example, the summary at Day 5 will denote the number of patients who had stenosis occur up to Day 5 or on the Day 5 visit. Similarly, the Day 29 summary will denote the number of patients with stenosis events that occurred after Day 5, and up to Day 29 (inclusive of Day 29).

The time of first stenosis (in days) will be summarized and calculated as number of days from HAV implantation to date of first stenosis event: Date of Stenosis – Date of Day 1 + 1. Patients who did not have a stenosis event will not contribute a value for this summary.

Please note, the clinical duplex will be recorded for all visits. Results after Month 12 **will not** be summarized in tables and will be provided in the listings.

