4.4.4 Other Efficacy Variables

High Resolution Ultrasound

Doppler ultrasound (HAV patency) high resolution ultrasound data will be listed.

Time to loss of patency

Time after first implantation of HAV until loss of patency (primary, primary assisted and secondary) will be separately presented in tables using descriptive statistics. The time to loss of patency will be verified during the DRM using all data from the CRF including the information used for patency rates at each visit and information on any AEs and consequent interventions.

Patients discontinued early with the HAV still patent, will be censored at that timepoint.

The median times (or the lower quartile – in case the median is unable to be estimated) will be presented together with the respective 95% CIs using Kaplan-Meier estimates. In case of small numbers of events these analyses may be skipped.

For the 1-year interim analysis, time to loss of patency will be reviewed for the first 12 months, and rates of 3, 6, and 12 months will be presented. For the final analysis, time to loss of patency will be reviewed for the entire study and rates of 3, 6, 12, 24, 36, 48, and 60 months will be presented.

Focused vascular assessment exam will be listed.

Angiography and Endothelium-dependent, flow-mediated vasodilation data will be listed.

5 Safety Analysis

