4.4 Efficacy Analysis

4.4.1 Analysis of Primary Efficacy Parameters

Primary, primary assisted, and secondary patency rates of the HAV at Month 12 month and at all other post-surgery visits with evaluation of patency will be described.

Patency is defined as the functional patency until any type of intervention;

Primary patency is defined as the access patency until any type of intervention.

Primary assisted patency is defined as an HAV still working without thrombosis.

Secondary patency is defined as the functional patency, with or without preceding successful interventional or surgical procedures to maintain or reestablish patency, until either final failure or the access is abandoned.

Early discontinued patients prior to the visit of interest will be determined as being non-patent irrespective of the reason for discontinuation.

The assignment to a patency (yes/ no) (primary, primary assisted, secondary patency) will be verified during the DRM using all data of case report form (CRF) sections referring to HAV

08 September 2016

Statistical Analysis Plan	Final Analysis
CLN-PRO-004	12/19

patency, clinical examination of the HAV site, doppler ultrasound assessment of HAV patency, HAV intervention, premature discontinuation, and adverse events.

Patency rates will be presented with frequency tabulations showing patient numbers and patency rates for month 12.

Clopper-Pearson confidence limits will be presented for frequency counts of patency rates.

Hemodynamically significant stenosis (>70% by duplex ultrasound criteria): the absolute change from baseline (Day 1) values to all post-surgery visits of duplex ultrasound parameters will be summarized. Summary statistics will also be provided at each time point.

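### SAP v2.0 specifies no within-patient change in HAV diameter or flow, although Protocol 9.3 asks for change from Day 1 in the duplex parameters

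*Protocol*

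**What the plan says.** **Protocol.** Section 9.3 plans a change analysis as well as statistics at each time point: "The absolute change from baseline (Day 1) values to all post-surgery visits of duplex ultrasound parameters will be summarized". Section 7.5.2 gives the source of the Day 1 value: "High-resolution duplex ultrasound of the HAV will be performed to provide a baseline for follow up measurements". Section 7.4.2 repeats that modality: "High-resolution duplex ultrasound imaging will be performed at Day 1 and Months 3, 6 and 12". Clinical duplex is a separate examination that starts later. Section 7.1 describes it as "clinical assessment at all postoperative visits from Day 29 through Month 12 to assess HAV patency, mid HAV diameter and flow rate". CT angiography of the HAV also starts at Day 29 (section 7.4.1).

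**SAP version 2.0 (current).** Section 4.4.1, Efficacy Objective 2, says: "The duplex ultrasound parameters will be summarized by planned visit up to Month 12". The items named are stenosis and its location, aneurysm presence, flow rate and mid-bypass inner diameter. Clinical duplex after Month 12 goes to listings. Section 4.4.4 says: "Doppler ultrasound (HAV patency) high resolution ultrasound data will be listed". Section 4.4.2 promises a descriptive presentation of remodeling by CT angiography and ultrasound at Day 29 and Months 6, 12 and 60, without further detail. The general baseline rule at the start of section 4 is: "The closest non-missing values prior to implantation on Day 1 will be used as baseline values".

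**SAP version 1.0 (superseded, bound in the same file).** Its section 4.4.1 carried the protocol's analysis: "the absolute change from baseline (Day 1) values to all post-surgery visits of duplex ultrasound parameters will be summarized". This is background only; a difference between versions is not an error in itself.

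**The concern.** The protocol schedules a scan of the implanted HAV on Day 1 to serve as a reference and repeats that scan three times. The current SAP uses it only in a listing. HAV remodeling is a secondary efficacy endpoint (Protocol 4.2.2), and a question about how a conduit changes over time is one of within-patient change. Means at separate visits answer it only if the same HAVs are measured each time.

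That is doubtful here. Fifteen patients were recruited (SAP 1.5). In the sponsor's earlier PAD study, 7 of 20 patients left before completing two years, four of them after HAV occlusion (Protocol 2.4.3). If HAVs leave the scanned set, a visit mean can move without any conduit changing, or stay still while conduits dilate. With nothing specified, the reference scan, modality and segment for any change score would be chosen after the data are seen.

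**Working it through.** The documents give no SD, correlation or target precision for any duplex parameter, so there is no figure to reproduce. The check sets the texts side by side and then shows the scale.

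**1. Is a paired analysis possible from the planned visits?**

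| Examination | First HAV measurement | Later measurements | SAP v2.0 output |
|---|---|---|---|
| High-resolution duplex | Day 1, intraoperative | Months 3, 6, 12 | Listing |
| Clinical duplex | Day 29 | Months 3, 6, 9, 12, then every 6 months to 54 | By-visit summary to Month 12, then listing |
| CT angiography | Day 29 | Months 6, 12, 60 | Descriptive, parameters not named |

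Same-modality pairs exist by design in every row, and no row has a change score. By contrast, SAP 4.4.2 plans change from baseline for VascuQol, ABI and the 6 minute walk test.

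**2. What do by-visit means do when HAVs drop out?** Take a hypothetical set of 15 HAVs with starting diameters evenly spaced from 5.3 to 6.7 mm (mean 6.0), each dilating by exactly 0.5 mm.

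- All 15 scanned again: 6.5 - 6.0 = 0.5 mm.
- Four largest lost: the remaining 11 started at a mean of 5.8, now 6.3; 6.3 - 6.0 = 0.3 mm.
- Four smallest lost: the remaining 11 started at a mean of 6.2, now 6.7; 6.7 - 6.0 = 0.7 mm.

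The mean paired change is 0.5 mm in all three cases. The diameters and the loss of four are assumptions chosen to show the mechanism; they do not predict this trial.

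**3. What does pairing do for precision?** With complete data the difference in visit means equals the mean paired change, so only the standard error differs. With equal variance and n HAVs at both visits, the SE of the paired change is SD·√(2(1-r)/n). Treating the visits as independent gives SD·√(2/n). The ratio is √(1-r):

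- r = 0.3: √0.7 = 0.84
- r = 0.5: √0.5 = 0.71
- r = 0.9: √0.1 = 0.32

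For n = 15, the 95% half-width for mean change is t(0.975, 14)/√15 = 0.55 SDs of the change. In units of the between-patient SD this is 0.66, 0.55 and 0.25 at r = 0.3, 0.5 and 0.9, against 0.75 for the unpaired contrast. At r = 0 pairing gains nothing (0.78 against 0.75). With 10 pairs the half-width is 0.72 SDs of the change. A reader who has only visit SDs cannot recover the SD of the change.

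**The case against.** **Dilatation is still reported.** A reader might infer that it is never estimated. The documents do not support that. SAP v2.0 summarizes mid-bypass diameter and aneurysm presence by visit to Month 12, tabulates aneurysm and pseudoaneurysm as HAV complications, presents remodeling descriptively, and lists long-term aneurysmal dilatation. The remodeling text does not exclude a change score; it simply does not specify one.

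**The stability objective is about events.** Protocol 3.2 frames mechanical stability as freedom from aneurysmal degeneration. Tabulated aneurysms address that directly, and mean change at mid-HAV could miss focal dilatation elsewhere. This stands. Event counts are limited evidence (0 of 15 leaves a two-sided 95% Clopper-Pearson upper limit of 1 - 0.025^(1/15) = 21.8%), but change scores would complement them, not replace them.

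**The baseline rule blocks nothing at present.** It is tempting to say that a pre-implantation baseline makes every HAV change missing. The rule is a general default, and SAP v2.0 plans no duplex change score to which it would apply. The omission is the gap. The rule becomes an obstacle only once the analysis is restored.

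**The departure may be declared.** SAP v2.0 has a section on changes from the protocol that is not in the text available for review, and Protocol section 9 leaves details of the planned descriptive statistics to the SAP. The departure therefore cannot be called undeclared.

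**The study is small and exploratory.** With 15 patients, pairs could be read from the listings. This stands in part and limits the severity, but a listing does not settle which scan is the reference.

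**Pairing has limits.** It removes the shift in case mix but not the selective loss of occluded HAVs, which still contribute no later value. The SAP also plans no formal contrast between visits, so the SE ratios describe only what a reader might do informally.

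**Conclusion.** The mismatch is real and can be read from the text: Protocol 9.3 plans change from Day 1 in duplex parameters, Protocol 7.5.2 schedules the scan to supply it, and SAP v2.0 specifies no within-patient change in HAV diameter or flow. What is lost is a defined, paired description of remodeling and gradual diameter change. Aneurysm reporting is not lost.

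The size cannot be fixed from the documents. The shifts of 0.2 mm either way in the example rest on assumed diameters and dropout, and the SE ratios of 0.84 to 0.32 rest on an assumed correlation of 0.3 to 0.9. No test or power statement is affected, because the study has none. This should be corrected as an inexpensive repair; it does not threaten the trial's main conclusions.

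**What to change.** In SAP 4.4.1 and 4.4.2:

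- Add an HAV-specific exception to the general pre-implantation baseline rule.
- For high-resolution scans at Months 3, 6 and 12, use the Day 1 intraoperative high-resolution scan as reference. Name the diameter and flow parameters and the segment; the protocol does not itemize what this scan records.
- For clinical duplex and CT angiography, use Day 29, the first measurement of the HAV by either method.
- At each later visit, report paired within-patient change with the number of pairs and a 95% CI.
- State that paired change does not remove bias from HAVs lost to occlusion.
- Name the parameters and reference visit for the remodeling summary.

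If the sponsor prefers not to restore the analysis, the SAP should state and justify the departure from Protocol 9.3.

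The cost is SAP wording and one table, with no new procedures, since the scans are already scheduled. The downside is that intraoperative values may differ from ambulatory ones; the clinical duplex comparison from Day 29 helps to show whether they do.

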### 9.4. Other Analyses

All clinical parameters will be listed for all patients treated at each study visit. Descriptive statistics will be summarized for continuous outcomes such as age and BMI. If necessary, number and percentage of patients will be reported for categorical outcomes.

### 9.5. Sample Size Rationale

Up to 25 patients will be recruited into the study. As limited data evaluating the use of HAV to treat PAD are available, this Phase 2 study was designed to provide preliminary evidence of safety and efficacy.

The study is not powered to assess the efficacy of the HAV.

### 9.6. Interim analyses

There is no formal interim analysis.

# **10. STUDY MANAGEMENT AND DATA COLLECTION**

# **10.1.** Ethical Conduct of the Trial

This study will be conducted according to the protocol; 21 CFR Parts 11, 50, 54, 56, and 312; the World Medical Association Declaration of Helsinki (Appendix II) and Good Clinical Practice (GCP). Each investigator will conduct the trial according to applicable local or regional regulatory requirements.

# 10.2. Institutional Review Board

IRBs must be constituted according to the applicable state and federal requirements, including International Conference on Harmonization (ICH) GCP.

It is the responsibility of each investigator to submit the protocol, Investigator Brochure, subject informed consent, subject recruitment materials (if applicable), and other documentation as required by the IRB to his/her IRB for review and approval. A copy of the written approval must be provided to the CRO. The documentation should clearly mention the approval/favorable opinion of the protocol, the subject informed consent form, and subject recruitment materials (if applicable), including respective version dates. The written approval must be obtained from the IRBs and provided to the CRO prior to the release of clinical study supplies to the investigational site and commencement of the study. If any member of the IRB has direct participation in this trial, written notification regarding his or her abstinence from voting must also be obtained.

Each investigator must adhere to all requirements stipulated by his/her respective IRB. This includes notification to the IRB regarding protocol amendments, updates to the subject informed consent, recruitment materials intended for viewing by subjects, investigational new drug safety reports, SAEs and unexpected AEs, reports and updates regarding the ongoing review of the trial at intervals specified by the respective IRB, and submission of final study reports and summaries to the IRB.

